### **5.3. Treatment Compliance**

Not applicable for this study

### **5.4. Extent of Exposure**

Not applicable for this study

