## PROTOCOL AMENDMENTS

### **Amendment GEN-III (This document)**

**The overall reason for the amendment:** The aim of this roll-over study is to provide continued access to etravirine (ETR) for adult and pediatric subjects who continue to benefit from the use of ETR and who live in a country where ETR is either not commercially available, not reimbursed, or cannot be accessed through another source. As of this amendment, the follow-up in this study will be simplified for the reasons outlined below.

ETR is approved since 2008 in adults and since 2012 in children as of the age of 6 years and has a well-established safety profile. The collection of additional data in Study TMC125-C239 is unlikely to provide substantial additional information on ETR or to impact the risk-benefit assessment. The TMC125-C239 is a roll-over study that has been ongoing since December 2009 and provides already substantial long-term safety information on ETR. The parent trials TMC125-C206 and TMC125-C216 (in adults) ended in August 2008, after which the subjects were able to roll-over in the TMC125-C217 trial and subsequently into this roll-over study. Parent trial TMC125-C213 (in subjects aged 6 to 18 years) ended in August 2011. The parent trial TMC125-C234 (or IMPAACT trial P1090), conducted in subjects aged 1 to 5 years, is still ongoing and subjects still in this trial are expected to roll-over to Study TMC125-C239. By the time of entry in Study TMC125-C239, most of these subjects will have completed 48 weeks of ETR treatment plus an additional few years (up till 5 years) of follow-up in the parent trial. Hence, the subjects from Study TMC125-C239 have been on ETR for a significant amount of time. Therefore, the long-term safety of ETR has been properly assessed in these subjects, thereby allowing the study follow-up to be simplified for all subjects in this roll-over study.

As of this amendment, ETR will continue to be provided through this study until the subject can be switched to locally available ETR-based treatment regimens (ie, commercially available and reimbursed, or accessible through another source [eg, access program or government program]) or to local standard of care, as appropriate.

Furthermore, subjects aged 2 years and older are allowed to roll-over from parent trial TMC125-C234 and dosing instructions are added for pediatric subjects receiving another dose than provided in the dosing chart.

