### **3.4 Source Data**

The nature and location of all source documents is to be identified in the Source Document Verification Plan to ensure that all sources of original data required to complete the CRF are known and are accessible for verification by the monitor. If electronic records are maintained, the method of verification must be discussed and agreed upon between the investigational staff and the monitor.

The required source data are listed in the Source Document Verification Plan, and should include sequential notes containing at least the following information for each subject:

- subject identification (name, date of birth, gender);
- documentation that subject meets eligibility criteria, i.e., history, physical examination, and confirmation of diagnosis (to support inclusion and exclusion criteria);
- participation in trial (including trial number);
- trial discussed and date of informed consent/assent, a copy of the C/assent was given to the subject;
- dates of all visits;
- documentation that protocol specific procedures were performed;

- start and end date (including dose regimen) of trial medication (preferably drug dispensing and return should be documented as well);
- record of all reportable adverse events (see Section 1.4), and other safety parameters (start and end date, and preferably including causality and intensity);
- concomitant medication;
- date of trial completion and reason for early discontinuation, if applicable;

It is recommended that the author of an entry in the source documents is identifiable. Direct access to source documentation (medical records) must be allowed for the purpose of verifying that the data recorded on the CRF are consistent with the original source data.

After termination of data collection (see Figure 1), all visits and assessments will be performed per local standard of care and documented in the subject's medical records only. Data will no longer be recorded in the CRF.

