### 1.2. Trial Design

At the baseline visit, inclusion/exclusion criteria will be checked to confirm eligibility. Once eligibility criteria are met, subjects will either continue on the ETR dose they have received in the previous ETR trial or on an adjusted dose if deemed necessary by the investigator. For pediatric subjects, ETR dose adjustment will be based on weight using the dosing guidelines provided.

Assessment visits are recommended according to local generally accepted standard of care, but not less frequent than every three and six months for pediatric and adult subjects respectively. Adverse events leading to discontinuation or treatment interruption, adverse events at least possibly related to treatment with ETR, serious adverse events, and pregnancies will be recorded at each visit. In addition to the assessments described in the flowchart, additional assessments not included in this protocol can be done locally at the investigator's discretion as per local standard of care.

Treatment will be continued until one of the following criteria is met: the investigator determines that the subject no longer benefits from ETR treatment (e.g., based on viral load); treatment limiting toxicity; loss to follow-up; patient withdrawal of consent; pregnancy; termination of the program by the Sponsor; ETR becomes commercially available for the subject's indication, is reimbursed, or can be accessed through another source (e.g. access program, government program) in the region the subject is living in, whichever occurs first. A diagram of the study design is provided below in [Figure 1](#).

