### 2.2. Study Day and Relative Day

Study Day 1 or Day 1 refers to the start of the first study agent administration. All safety assessments at all visits will be assigned a day relative to this date.

Study day or relative day for a visit is defined as:

- Visit date - (date of Study Day 1) +1, if visit date is  $\geq$  date of Day 1
- Visit date - Date of Day 1, if visit date < date of Day 1

There is no 'Day 0'

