### **7.1. Adverse Events**

The verbatim terms used in the CRF by investigators to identify adverse events will be coded using the available version of the Medical Dictionary for Regulatory Activities (MedDRA version 23.0). Treatment-emergent adverse events are adverse events with onset during the treatment phase or

that are a consequence of a pre-existing condition that has worsened since baseline. If the event occurs on the day of the initial administration of study agent, and either event time or time of administration are missing, then the event will be assumed to be treatment emergent. If the event date is recorded as partial or completely missing, then the event will be considered treatment emergent unless it is known to be prior to the first administration of study agent based on partial onset date or resolution date. All reported adverse events will be included in the analysis. For each adverse event, the number and percentage of subjects who experience at least 1 occurrence of the given event will be summarized by treatment.

Summary tables will be provided by pediatric and adult subjects separately as well as overall for:

- Mortality
- Serious AEs (SAEs)
- AEs leading to discontinuation of treatment
- AEs possibly related to ETR
- All AEs

From the collected (S)AE data in TMC125-C239, the following events will be summarized:

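### SAP 5.4 plans no exposure summary in an open-ended trial, so adverse event percentages cannot reliably be read as rates or compared between the pediatric and adult columns

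*SAP*

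**What the plan says.** SAP 5.4 (Extent of Exposure) reads, in full, "Not applicable for this study". The same words stand under SAP 5.3 for compliance, which is not the issue here.

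For adverse events, SAP 7.1 states that "the number and percentage of subjects who experience at least 1 occurrence of the given event will be summarized by treatment", and that "Summary tables will be provided by pediatric and adult subjects separately as well as overall for" mortality, serious events, events leading to discontinuation, events possibly related to etravirine, and all events. SAP 7 limits categorical safety data to counts and percentages. The output list in SAP 7.3 has seven adverse event tables plus demographic, antiretroviral, disposition, COVID-deviation and weight outputs. None is a duration, patient-year or time-to-event output.

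Treatment is open-ended. SAP 1.2 says "Treatment will be continued until one of the following criteria is met", then lists subject-specific reasons for stopping; Protocol 5.1.1 does the same. The rationale for Amendment GEN-III says that the study "has been ongoing since December 2009 and provides already substantial long-term safety information on ETR".

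Much of what a duration table needs is already foreseen. SAP 2.2 fixes the start: "Study Day 1 or Day 1 refers to the start of the first study agent administration". Protocol 5.2.5 requires the discontinuation date on the CRF. Protocol Part II, 3.4 requires "start and end date (including dose regimen) of trial medication" in the source documents.

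**The concern.** The share of subjects with at least one event grows with time under observation. Where everyone is followed for the same planned period, that period supplies the missing denominator. Here no such period exists: treatment can end after a single visit interval or continue for years. A table reading 20% therefore does not tell the reader whether the event is frequent or whether the subjects were followed for a long time.

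Two uses of the results suffer. One is any statement about long-term safety, which needs a statement of how long. The other is the comparison that the layout invites: pediatric, adult and pooled columns are printed side by side, and they can be compared only if follow-up was similar. The SAP also says that the data may go into Safety Updates (SAP 1.4), where exposure would normally be needed to interpret them.

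**Working it through.** The plan states no sample size, rate or exposure figure, so there is nothing of its own to reproduce. The check has four steps.

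**1. Can follow-up be recovered from the planned outputs?** Only roughly.
- The weight tables (SAP 7.2; TSFVIT01a and b) give N per 3-month window for pediatric subjects and per 6-month window for adults, which approximates retention by group. However, Flowchart 1 does not mark weight at the Final/Withdrawal Visit, and the COVID-19 appendix says that weight is not taken at remote visits.
- The disposition table (SAP 5.2) counts reasons for stopping, not time.
- The listings may carry dates, but they leave the summary to the reader.

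**2. Can follow-up be assumed equal?** No. According to the GEN-III rationale, the adult parent trials ended in August 2008, with an intermediate roll-over trial after them; C213 ended in August 2011; and C234 was still running. Entry was therefore staggered. One stopping reason, local availability or reimbursement, varies by region. Nothing in the documents shows which age group was followed longer.

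**3. How much could it matter?** The rates and durations below are assumptions. The longest duration is elapsed trial time: December 2009 to 22 July 2019 is 9.56 to 9.64 years, taken as 9.6. It is not any subject's known follow-up, and CRF collection runs on to the next planned visit after approval of the amendment.

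With constant rate r per year and follow-up t, the expected share with an event is 1 − exp(−r·t). For example, 1 − exp(−0.05 × 9.6) = 1 − exp(−0.48) = 38.1%.

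| Rate per 100 patient-years | 1 year | 3 years | 6 years | 9.6 years |
|---|---|---|---|---|
| 2 | 2.0% | 5.8% | 11.3% | 17.5% |
| 5 | 4.9% | 13.9% | 25.9% | 38.1% |
| 10 | 9.5% | 25.9% | 45.1% | 61.7% |

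In reverse, r = −ln(1 − p)/t. For p = 20%, −ln(0.8) = 0.223, giving these rates per 100 patient-years:

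| Printed percentage | All followed 1 year | 3 years | 6 years | 9.6 years |
|---|---|---|---|---|
| 10% | 10.5 | 3.5 | 1.8 | 1.1 |
| 20% | 22.3 | 7.4 | 3.7 | 2.3 |

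**4. If rates are added, what must match?** SAP 7.1 says "All reported adverse events will be included in the analysis", and the visit 4 weeks after withdrawal collects events. That visit adds 28/365.25 = 0.077 year for a subject who attends: 7.7% of 1 year, 0.8% of 9.6 years. The effect on person-time is small; what matters is that the events counted and the time counted come from the same window. Who attends is described in two ways: Flowchart 1, footnote b, limits it to drop-outs due to an adverse event, while Protocol 5.2.5 extends it to all premature discontinuations not continuing etravirine. These passages need reconciling.

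**The case against.** The strongest reply is that the SAP does what the protocol asks. Protocol 5.7.3.1 requests mortality, serious events, events leading to discontinuation, related events and reasons for stopping; it does not ask for exposure or rates. The objective is drug provision, there is no hypothesis, and no comparison of adults with children is planned. The phrase about long-term safety comes from the reason for simplifying follow-up and is not an objective. All of this stands. It makes the point a reporting improvement and not a conflict between SAP and protocol.

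It is also fair that the weight tables give each group an approximate retention curve, so follow-up is not wholly invisible, and that the illustration would apply to any open-ended trial.

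A rate for every adverse event table would go too far. Under Protocol Part II, 1.4, non-serious events that are neither possibly related to etravirine nor a cause of interruption or discontinuation are collected only where local regulations require. That affects the all-event and grade 3-4 tables. It also affects the events of interest, which are drawn from the same data and include non-serious terms such as rash and erythema. Person-time from countries that do not collect such events would dilute those rates.

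Finally, the dates are not quite ready to use. The medication dates in Protocol Part II, 3.4 are source data and not shown to be CRF fields, and the CRF discontinuation date sits under withdrawal from the trial, so it need not be the last intake.

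**Conclusion.** The point holds as a cheap improvement that should be made. SAP 5.4 is an explicit decision against an exposure summary in a trial where follow-up is unequal by design, and nothing else planned summarizes duration or patient-years. The percentages remain valid as the share of subjects affected while observed. They cannot reliably be read as rates or compared between the age columns.

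A reader might go further and infer that the percentages are wrong, or that the adult-pediatric contrast is biased in a known direction. The documents support neither: they give no follow-up distribution, no event counts and no difference in duration between the groups. On the assumed rates, one underlying risk can print as anything from 4.9% to 38.1% (at 5 per 100 patient-years, 1 to 9.6 years). That rests on a constant rate and assumed durations, and shows what could happen, not what did.

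**What to change.** **Main change.** Replace SAP 5.4 with one table of etravirine treatment duration in C239: N, mean, SD, median, range and total patient-years, for pediatric, adult and overall.
- *Groups:* use one reconciled definition. Protocol 5.7.3 classifies by age at entry to the current trial; SAP 2.4 uses age at entry to the previous trial.
- *Start:* first study agent administration in C239.
- *End:* last recorded etravirine intake where available. Otherwise use the CRF discontinuation date, the last CRF contact for subjects lost to follow-up, or the Final/Withdrawal Visit for subjects who continue.
- *Notes:* state that interruptions are not subtracted. State how many ITT subjects have no CRF follow-up because they entered from C234 under Amendment 3 (Protocol 5.1.1 and 5.4.2). The Introduction describes C234 as 26 children, so the number is at most 26 on that count.

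**Optional addition.** Beside n (%), give incidence per 100 patient-years (subjects with a first event, divided by time to first event or end of window) with exact Poisson 95% confidence intervals. Restrict it to the categories collected in all countries: mortality, serious events, events at least possibly related to etravirine, and events leading to discontinuation. Use one stated window for events and time: either on-treatment only, or including time to the follow-up visit for those who attended. Leave the all-event, grade 3-4 and events-of-interest tables as n (%). Note that such rates assume constancy over time and cover only C239 time in subjects already treated in parent trials, so they do not by themselves allow comparison with another study.

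**Cost.** The main change is SAP wording, one table and a rule for partial dates. The optional rates need time to first event for each category, which is modest extra programming. If only one part is adopted, the duration table is the one to keep.

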### **5.5. Protocol Deviations**

If captured, major protocol deviations will be defined. A listing of subjects with a major protocol deviation will be provided.

### **5.6. Prior and Concomitant Medications**

Will be summarized by CMDECODE antiretroviral category

### **5.7. Medical history**

Not applicable

## **6. EFFICACY**

N/A

## **7. SAFETY**

All safety analyses will be based on the safety analysis set.

Safety data of adult and pediatric subjects will be analyzed separately as well as overall.

For all continuous safety variables, descriptive statistics will include the N, mean, standard deviation, median, minimum, and maximum. Categorical variables will be summarized using frequency counts and percentages.

### **7.1. Adverse Events**

The verbatim terms used in the CRF by investigators to identify adverse events will be coded using the available version of the Medical Dictionary for Regulatory Activities (MedDRA version 23.0). Treatment-emergent adverse events are adverse events with onset during the treatment phase or

that are a consequence of a pre-existing condition that has worsened since baseline. If the event occurs on the day of the initial administration of study agent, and either event time or time of administration are missing, then the event will be assumed to be treatment emergent. If the event date is recorded as partial or completely missing, then the event will be considered treatment emergent unless it is known to be prior to the first administration of study agent based on partial onset date or resolution date. All reported adverse events will be included in the analysis. For each adverse event, the number and percentage of subjects who experience at least 1 occurrence of the given event will be summarized by treatment.

Summary tables will be provided by pediatric and adult subjects separately as well as overall for:

- Mortality
- Serious AEs (SAEs)
- AEs leading to discontinuation of treatment
- AEs possibly related to ETR
- All AEs

From the collected (S)AE data in TMC125-C239, the following events will be summarized:

#### Skin events

Skin events of interest will be assigned to categories from the following list:

- ‘(Serious) Rash Cases’: a predefined list of selected PTs used for the post-marketing safety monitoring, is used to identify (serious) cases of Rash.

Acrodynia	Rash generalised
Drug eruption	Rash macular
Erythema ab igne	Rash maculo-papular
Erythema	Rash maculovesicular
Erythema elevatum diutinum	Rash morbilliform
Erythema toxicum neonatorum	Rash neonatal
Fixed eruption	Rash papular
Generalised erythema	Rash pruritic
Lupus miliaris disseminates faciei	Rash pustular
Mucocutaneous rash	Rash rubelliform
Necrolytic migratory erythema	Rash scarlatiniform
Rash	Red man syndrome
Rash erythematous	Rash vesicular

- ‘(Severe) Cutaneous Reactions’: the MedDRA SMQ (Severe) Cutaneous Adverse Reactions [Broad scope SMQ code: 20000020], which includes Stevens-Johnson Syndrome, is used to identify cases.
- ‘Angioedema’: the MedDRA SMQ Angioedema (SMQ, broad) is used to identify cases.

- Cardiac
- Hepatobiliary

### Hepatic events

Hepatic events of interest (or ‘Hepatotoxicity’) will be assigned to the subcategories from the following list, with relevant SMQs to identify cases:

- “Cholestasis and jaundice”: Cholestasis and jaundice of hepatic origin, broad (SMQ code: 20000009),
- “Hepatic Failure, fibrosis and cirrhosis and other”: Hepatic failure fibrosis and cirrhosis and other liver damage-related conditions, broad (SMQ code: 20000013),
- “Hepatitis non-infectious”: Hepatitis non-infectious, broad (SMQ code: 20000010),
- “Liver related investigations, signs and symptoms”: Liver related investigations signs and symptoms, broad (SMQ code: 20000008).

- Neuropsychiatric

In addition to the summary tables, listings will be provided for subjects who:

- Mortality
- Had SAEs
- Had AEs leading to discontinuation of treatment

## 7.2. Clinical Laboratory Tests and Vital Signs Findings

### Missing baseline values:

The only reference time point for the weight analysis will be baseline. If there is no baseline value available, no changes will be calculated. Observed and change from baseline in weight by visit will be summarized by pediatric and adult subjects separately. [Table 2](#) and [Table 3](#) show the definition of windows used for the weight analysis for pediatric and adult, respectively.

Table 2: Definition of windows for weight (pediatric subjects)

Phase	Visit	Target day	Analysis time point	Time interval (days)
Baseline	1	1	Baseline	<=1
Treatment	2	90	Month 3	2 to 135
	3	180	Month 6	136 to 225
	4+	XX*30	Month XX	[XX*30 days – 44 to XX*30 days + 45]

Table 3: Definition of windows for weight (adult subjects)

Phase	Visit	Target day	Analysis time point	Time interval (days)
Baseline	1	1	Baseline	<=1
Treatment	2	180	Month 6	2 to 270
	3	360	Month 12	271 to 450
	4+	XX*30	Month XX	[XX*30 days – 89 to XX*30 days + 90]

If two (or more) measurements fall within the same time interval, the measurement closest to the target day (in case of equal distances, latest measurement takes precedence) is used for the analysis displays and graphics in order to have only one measurement per subject per analysis time point. However, all data are presented in the listings.

The number of days in the treatment is defined as:

relday = visit day – reference day+1 for visits on or after the reference

relday = visit day – reference day for visits before the reference where the reference day equals the actual start date of intake of ETR.

### 7.3. Overview of statistical output

COVID related deviations	
TCOV01	COVID-related deviations: Tabulation
LCOV01	COVID-related deviations: Listing
Demographics	
TDEM01	Demographics and baseline characteristics
LDEM01	Listing of demographics and baseline characteristics
Prior and Concomitant Medications	
TSICM01	Prior ARV Therapies; Individual ARVs
TSICM02a	Initial OBR Therapies Individual ARVs
TSICM02b	Initial OBR Therapies Combinations of ARVs
Disposition	
TDIS01	Disposition

LDIS01	Listing of disposition
Safety	
TSFAE01	Adverse Events: Summary Table
TSFAE02	Adverse Events: Tabulation of All Events by System Organ Class and Preferred Term
TSFAE03	Frequency (%) of Serious Adverse Events
TSFAE04	Frequency (%) of Grade 3-4 Adverse Events (Regardless of Causality)
TSFAE05	Frequency (%) of Adverse Events at Least Possibly Related to Etravirine
TSFAE06	Frequency (%) of Adverse Events Leading to Permanent Stop of Study Medication
TSFAE07	Adverse Events of Interest by Event of Interest Group
LSFAE01	Adverse Events: Summary Listing of All Events
LSFAE02	Adverse Events: All Events with Grade 3 to 4 Toxicity
LSFAE03	Adverse Events: All Serious Events
LSFAE04	Adverse Events: All Events at Least Possibly Related to Study Medication
LSFAE05	Adverse Events of Interest: Summary Listing of All Events of Interest
LSFAE06	Adverse Events: All Events Leading to Permanent Stop of Study Medication
TSFVIT01a	Observed and Change from Baseline in Weight by visit (pediatric)
TSFVIT01b	Observed and Change from Baseline in Weight by visit (adult)
TSLWT01a	Listing: Weight (pediatric)
TSLWT01b	Listing: Weight (adult)
